
### 3.7. Overall Study Rationale and Objectives

A maculopapular rash with eosinophilia is an expected effect of alpelisib that limits medication adherence and efficacy, and patient quality of life. We have identified one strategy that treated the alpelisib-induced rash with eosinophilia: an inhibitor of the IL-5ra. There is extensive pre-clinical and anecdotal clinical data supporting the presence of eosinophilia in alpelisib rash and the role of eosinophils in drug reactions, hence inhibition of these cells may prevent alpelisib rash. In this trial, we will formally test the efficacy and safety of eosinophil depletion with the IL-5 receptor inhibitor benralizumab in postmenopausal women and men with histologically-confirmed, HR-positive, HER2-negative, *PIK3CA*-mutant MBC. The objectives are as follows:

**Primary Objective:** To determine if prophylactic IL-5 receptor inhibition results in a lower incidence of alpelisib rash when compared to historical controls.

#### Secondary Objectives

1. To determine the effect of prophylactic anti-IL-5 receptor inhibition on alpelisib dose interruption or modification when compared to historical controls as determined by relative dose intensity (RDI) during the initial 4 weeks of therapy (4W-RDI).
2. To determine the effect of prophylactic anti-IL-5 receptor inhibition on quality of life when compared to historical controls using the Functional Assessment of Cancer Therapy—Breast (FACT-B) and the PRO-CTCAE.
3. To determine the effect of prophylactic anti-IL-5 receptor inhibition on cumulative steroid dose when compared to historical controls.
4. To determine the effect of prophylactic anti-IL-5 receptor inhibition on time to development of alpelisib grade  $\geq 2$  rash when compared to historical controls.
5. To determine the safety of anti-IL-5 receptor inhibition and historical controls in patients receiving alpelisib, defined as adverse events definitely, possibly or probably related to anti-IL-5 receptor inhibition or historical controls
6. To determine the effect of anti-IL-5 receptor and historical controls on non-skin alpelisib-related adverse events (eg. nausea, diarrhea, vomiting, anorexia, fatigue, weight loss).
7. To determine the overall response rate (ORR) and progression free survival (PFS) at 6 and 12 months post treatment initiation.

#### Exploratory Objectives

1. Explore the change in serum and skin inflammatory markers from baseline to 4 weeks (using non-invasive skin tape for skin).
2. Explore the change in histologic markers from skin biopsies in patients with rash, including eosinophil counts, CD4/8 count, IL-5, PI3 kinase pathway activation; at rash onset and at 28 days.

## 4.0 OVERVIEW OF STUDY DESIGN/INTERVENTION

### 4.1 Design

This is a prospective, MSK investigator-initiated, multi-center, open-label, phase 2 trial testing the efficacy and safety of one interventions that targets interleukin 5 receptors during PI3K inhibitor therapy in patients with HR-positive, HER2-negative, *PIK3CA* mutant MBC receiving first or second line therapy. Study participants (n=63) will be treated with benralizumab in combination with SOC endocrine therapy (fulvestrant or AIs) and PI3K inhibition (alpelisib). Crossover will not be allowed. The primary endpoint is the grade ≤1 rash rate at 4 weeks.

Postmenopausal women and men with histologically-confirmed, HR-positive, HER2-negative, *PIK3CA* mutant MBC who have received no more than 1 line of endocrine-based therapy in the metastatic setting will be eligible. Study recruitment will be done by MSK and the participating institutions. Patients will be screened by members of the institution's breast oncology service. Those deemed eligible will complete baseline skin exam, skin tape stripping, blood work and urinalysis (See section 9.0).

### 4.2 Intervention

Eligible patients will undergo screening and baseline procedures per the pretreatment study schedule (Section 8.0). Study inclusion and exclusion criteria will be applied per section 6.0. Patients will undergo SOC histologic assessment and genomic analysis, and research blood testing. Once eligibility is confirmed, patients will receive benralizumab.

Patients will receive fulvestrant or AIs and PI3K inhibition (alpelisib) per SOC (fulvestrant on days 1, 15, 29 and monthly thereafter; AIs on a daily continuous basis). Participants will receive one injection of benralizumab 30mg subcutaneously on day -1.

Adherence, tolerance, and adverse effects (AEs) of the therapeutic agents will be evaluated at weeks 2 and 4. Research staff and investigators will review adherence and tolerance medications, AEs or intolerance, and collect skin tape strips, urinalyses, and research bloods or biopsies per Section 11.0.

Safety will be evaluated in this study through the monitoring of all serious and non-serious AEs, graded according to National Cancer Institute Common Terminology Criteria for Adverse Events, version 5.0 (NCI CTCAE v5.0).

## 5.0 THERAPEUTIC/DIAGNOSTIC AGENTS & NON-THERAPEUTIC ASSESSMENTS

### Alpelisib

#### a. Dosage and administration

Alpelisib is indicated in combination with fulvestrant for the treatment of postmenopausal women, and men, with hormone receptor (HR)-positive, human epidermal growth factor

receptor 2 (HER2)-negative, PIK3CA-mutated, advanced or metastatic breast cancer as detected by an FDA-approved test following progression on or after an endocrine-based regimen. The recommended dose of Alpelisib is 300 mg (two 150 mg film-coated tablets) taken orally, once daily, with food. Patients should take their dose of Alpelisib at approximately the same time each day. Alpelisib tablets are swallowed whole (tablets should not be chewed, crushed or split prior to swallowing). No tablet should be ingested if it is broken, cracked, or otherwise not intact. If a dose of Alpelisib is missed, it can be taken with food within 9 hours after the time it is usually taken. After more than 9 hours, the dose is skipped for that day and resumed the next day.

b. Preparation

Alpelisib has been formulated as immediate-release tablets for oral administration. The tablet consists of a mixture of alpelisib drug substance with microcrystalline cellulose, low substituted hydroxypropyl cellulose, croscarmellose sodium, colloidal silicon dioxide (anhydrous), and magnesium stearate. The clinical trial tablets will be supplied in 150-mg (caplet) dose strengths.

c. Storage

Alpelisib dosage forms and strengths include 50 mg, 150 mg, and 200 mg film-coated tablets.

300 mg daily dose: Each carton contains 2 blister packs. Each blister pack contains a 14-day supply of 28 tablets (28 tablets, 150 mg alpelisib per tablet).

250 mg daily dose: Each carton contains 2 blister packs. Each blister pack contains a 14-day supply of 28 tablets (14 tablets, 200 mg alpelisib per tablet and 14 tablets, 50 mg alpelisib per tablet).

200 mg daily dose: Each carton contains 1 blister pack. Each blister pack contains a 28-day supply of 28 tablets (28 tablets, 200 mg alpelisib per tablet).

Store at 20°C to 25°C (68°F to 77°F), excursions permitted between 15°C and 30°C (59°F and 86°F).

### **Benralizumab**

Benralizumab is FDA approved as a maintenance treatment of patients 12 years or older with severe asthma and an eosinophilic phenotype and will be provided by AstraZeneca. Benralizumab use in this study will be IND exempt (request submitted) The pathology of severe asthma with eosinophilic phenotype is also denoted as TH2-high phenotype.

a. Dosage and administration

Benralizumab is an IL-5R inhibitor to be administered as a single dose of 30mg subcutaneously at least 1 day and no more than 7 days prior to alpelisib initiation.

b. Preparation

Check the expiration date (EXP). Do not use if the expiration date has passed. Let benralizumab warm up at room temperature between 68°F to 77°F (20°C to 25°C) for about 30 minutes before giving the injection. Do not warm the benralizumab PEN in any other way. For example, do not warm it in a microwave or hot water, or put it near other heat sources. Use benralizumab within 14 days of removing from the refrigerator. After 14 days, throw away the benralizumab PEN. Do not remove the cap until you have reached Step 6. Look at the liquid in the benralizumab PEN through the viewing window. The liquid should be clear and colorless to slightly yellow. It may contain small white particles. Do not inject benralizumab if the liquid is cloudy, discolored, or contains large particles. You may see small air bubbles in the liquid. This is normal. You do not need to do anything about it. the recommended injection site is the front of your thigh or the lower part of your stomach (abdomen). A caregiver may inject you in the upper-arm, thigh, or abdomen. Do not try to inject yourself in the arm. For each injection, choose a different site that is at least 1-inch (3-cm) away from where you last injected. Do not inject: into the 2-inch (5-cm) area around your belly-button, where the skin is tender, bruised, scaly or hard, into scars or damaged skin, through clothing. Wash your hands well with soap and water. Clean the injection site with an alcohol wipe in a circular motion. Let it air dry. Do not touch the cleaned area before injecting. Do not fan or blow on the cleaned area. Hold the benralizumab PEN with 1 hand. Carefully pull the cap straight off with your other hand. Put the cap aside to throw away later. The green needle guard is now exposed. It is there to prevent you from touching the needle. Do not try to touch the needle or push on the needle guard with your finger. Do not try to put the cap back on the benralizumab PEN. You could cause the injection to happen too soon or damage the needle. Complete the following steps right away after removing the cap. You can either gently pinch at the injection site or give the injection without pinching the skin. Inject benralizumab at a 90° angle. Hold the benralizumab PEN in place for the entire injection. Do not change the position of the benralizumab PEN after the injection has started. Check the viewing window to make sure all the liquid has been injected.

c. Storage

Store benralizumab in a refrigerator between 36°F to 46°F (2°C to 8°C) in its original carton until you are ready to use it. benralizumab may be kept at room temperature between 68°F to 77°F (20°C to 25°C) for a maximum of 14 days. • Once removed from the refrigerator and brought to room temperature, benralizumab must be used within 14 days or thrown away (disposed of). Do not use if: • it has been frozen • it has been dropped or damaged • the security seal on the carton has been broken • the expiration date (EXP) has passed. Do not • shake your benralizumab PEN • share or reuse your benralizumab PEN • expose your benralizumab PEN to heat. Each benralizumab PEN contains a single dose of benralizumab and cannot be reused. • Put your used benralizumab PEN in a FDA-cleared sharps disposal container right away after use.

## Drug Accountability

Memorial Sloan Kettering Cancer Center  
[name]  
[name]

The site investigator or designee is responsible for maintaining accurate records (including dates and quantities) of study drug received, patients to whom study drug is dispensed (patient-by patient dose-specific accounting), and study drug lost or accidentally or deliberately destroyed. The Investigator or its designee must retain all unused or expired study supplies until the Sponsor or its designee has confirmed the accountability data.

Unused study drug must be kept in a secure location for accountability and reconciliation by the PI or its designee. The site investigator or its designee must provide an explanation for any destroyed or missing study drug or study materials.

Unused study drug may be destroyed on site, per the site's standard operating procedures, but only after the PI or its designee has granted approval for drug destruction. The PI or its designee must account for all study drug in a formal reconciliation process prior to study drug destruction. All study drug destroyed on site must be documented. Documentation must be provided to the PI or its designee and retained in the Investigator's study files. If a site is unable to destroy study drug appropriately, the site can return unused study drug to the PI or its designee upon request. The return of study drug or study drug materials must be accounted for on a Study Drug Return Form provided by the PI or its designee.

All study drug and related materials should be stored, inventoried, reconciled, and destroyed or returned according to applicable state and federal regulations and study procedures.

The benralizumab will be provided by AstraZeneca. The alpelisib will be provided by Novartis.

### **Patient Compliance**

Patients will be given study drug, dosing diaries, and detailed instructions on how to take medications at home. Patients will be instructed to return all used and unused study drug containers at each study visit. Patient compliance with the dosing schedule will be assessed by reconciliation of the used and unused study drug at each clinic visit and review of the dosing diaries. The quantity of dispensed and returned study drug must be recorded on a study drug accountability log. Compliance will be monitored and documented by site personnel on the appropriate form. The site personnel will determine the patient's adherence to the dosing schedule by reviewing the dosing diaries and questioning the patient about any discrepancies, recording the number of tablets and strengths returned, the date returned, and determining treatment compliance before dispensing new medication to the study patient.

## **6.0 CRITERIA FOR PARTICIPANT ELIGIBILITY**

### **6.1 Participant Inclusion Criteria**

Memorial Sloan Kettering Cancer Center  
[name]  
[name]

1. Histologically confirmed metastatic HR-positive, HER2-negative breast cancer. HR positive is defined by ER status >10% immunohistochemical (IHC) staining of any intensity.
2. Must be scheduled to receive SOC endocrine therapy (alpelisib plus fulvestrant or AIs)
3. Presence of one or more activating *PIK3CA* mutations in tumor tissue.
4. Measurable disease per RECIST v1.1 OR at least one predominantly lytic bone lesion must be present.
5. Written informed consent provided
6. Female or male  $\geq 18$  years of age
7. Eastern Cooperative Oncology Group performance status of 0 or 1.
8. Life expectancy  $\geq 6$  months.
9. Adequate organ and marrow function as defined below:
  - Hemoglobin  $\geq 8.0$  g/dL (without blood transfusion within 7 days of laboratory test used to determine eligibility)
  - Absolute neutrophil count  $\geq 1.0 \times 10^9/L$  (without granulocyte colony stimulating factor support within 2 weeks of laboratory test used to determine eligibility)
  - Platelet count  $\geq 50 \times 10^9/L$  (without transfusion within 2 weeks of laboratory test used to determine eligibility)
  - Total bilirubin (TB)  $\leq 1.0 \times$  institutional upper limit of normal (ULN; Patients with known Gilbert's disease who have TB  $\leq 3 \times$  ULN may be enrolled)
  - Aspartate transaminase/alanine transaminase  $\leq 2.5 \times$  ULN with normal alkaline phosphatase ( $\leq 5 \times$  ULN for patients with liver metastases) OR  $\leq 1.5 \times$  ULN in conjunction with alkaline phosphatase  $>2.5 \times$  ULN
  - Creatinine  $\leq 1.5$  mg/dL.
10. Able to swallow oral medication.
11. Willing to be treated in the study arm and able to comply with the protocol for the duration of the study including undergoing treatment and scheduled visits and examinations
12. Women must be of postmenopausal status. Postmenopausal status is defined by any one of the following criteria:
  - Prior bilateral oophorectomy
  - Age  $\geq 60$  years
  - Age  $<60$  years and amenorrheic for at least 12 months (spontaneous cessation of menses for 12 consecutive months or more in the absence of chemotherapy, tamoxifen, toremifene, or ovarian suppression) and follicle-stimulating hormone and estradiol levels in the postmenopausal range without an alternative cause.

## 6.2 Participant Exclusion Criteria

1. Known hypersensitivity to alpelisib, fulvestrant or AIs, benralizumab, or to any of the excipients of alpelisib, fulvestrant or AIs, or benralizumab.
2. Concurrent malignancy (basal cell carcinoma of the skin, squamous cell carcinoma of the skin, or cervical cancer in situ that have undergone curative intent therapy are allowed)
3. Individuals with impaired decision making capacity.
4. Concurrent use of another investigational drug or device for the rash (i.e., outside of study treatment) during, or within 4 weeks of treatment.
5. Known use of anti-IL-5 agents or other biologics for the treatment of asthma which are known to decrease blood eosinophil levels within the past 12 weeks.

6. Known history of anaphylaxis to benralizumab therapy.
7. A helminthic parasitic infection diagnosed within 24 weeks prior to the first treatment, and assent when applicable, was obtained that had not been treated with, or has failed to respond to, standard of care therapy.
8. Known history of human immunodeficiency virus (HIV) infection or current chronic or active hepatitis B or C infection requiring treatment with antiviral therapy.
9. Active infection that would impair the ability of the patient to receive study treatment.
10. Women who are pregnant or breast-feeding.
11. Any condition which, in the investigator's opinion, makes the subject unsuitable for trial participation.
12. Oral corticosteroids at a dose of  $\geq 20$ mg/day prednisone or equivalent within 14 days expected to continue during alpelisib therapy.
13. More than 2 lines of endocrine-based therapy in the metastatic setting.

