## 1.0 PROTOCOL SUMMARY AND/OR SCHEMA

This is a multi-center, open-label, phase 2 trial testing the efficacy and safety of 2 interventions that target rash during PI3K inhibitor therapy in postmenopausal women and men with histologically-confirmed, hormone receptor (HR)-positive, HER2-negative, PIK3CA mutant metastatic breast cancer (MBC). A total of 63 patients will be enrolled into one arm: benralizumab 30mg in combination with standard of care (SOC) endocrine therapy (fulvestrant or AIs or aromatase inhibitors (AIs)) and PI3K inhibition (alpelisib). A total of 43 patients will be enrolled at MSKCC and a total of 20 patients will be enrolled at the participating external institutions (10 patients at Stanford University and 10 patients at Dana Farber Cancer Institute). The primary endpoint is the proportion of patients with grade  $\leq 1$  rash rate at 4 weeks.

**Patient Population:** The primary study population will be postmenopausal women and men with histologically-confirmed, HR-positive, HER2-negative, *PIK3CA* mutant MBC who have received no more than 2 lines of endocrine-based therapy in the metastatic setting.

**Design:** A multi-center, open-label, phase 2 trial testing the efficacy and safety of one interventions (one anti IL-5 receptor antibody and one antihistamine) that target the maculopapular rash during PI3K inhibitor therapy in patients with HR-positive, HER2-negative, *PIK3CA* mutant MBC receiving first or second line therapy. Study participants (n=112) will enrolled to one arm: benralizumab (anti-IL5ra) in combination with SOC endocrine therapy (fulvestrant or AIs) and PI3K inhibition (alpelisib). The primary endpoint is the grade  $\leq 1$  rash rate at 4 weeks. The study size is determined to compare the grade  $\leq 1$  rash rate at four weeks with historical controls. It has been reported that approximately 34% of patients receiving alpelisib will develop  $\geq$  grade 2 rash within the first 30 days. The corollary is that 66% of historical controls will have grade  $\leq 1$  rash within the first 30 days. An increase in rash control to approximately 88% is deemed to be clinically meaningful with the investigational agent under investigation (IL5r antibody). A sample size of 57 patients per group will achieve an 80% power to detect an odds ratio of 4.0 with respect to the primary endpoint. The proportion in the experimental group is assumed to be 0.66 under the null

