Previous analyses suggests that histamine producing cells and eosinophils have some role in alpelisib-related rash. All patients receiving alpelisib have a trend towards increased eosinophils, with a more pronounced effect in patients with rash. Interestingly, pre-treatment absolute eosinophil count may be lower in patients who develop rash. We also found that patients developing rash had a statistically significant increase in eosinophils after 2 weeks of

receiving alpelisib ( $p < 0.05$ ) (below, left). This has also been demonstrated in phase 1

study of alpelisib in combination with fulvestrant or Als (below, right). Prospective analyses and anecdotal experience at MSK with over 100 patients has revealed that 90% of rash develops within the first 4 weeks. Indeed, the median time to onset of grade 3-4 rash was 13 days in the pivotal SOLAR-1 trial.

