Targeting alpelisib rash with an IL-5 receptor antibody represents a paradigm shift, as it would be amenable to prophylactic (if very frequent or in populations at risk) and effective reactive therapies, precluding the need for alpelisib dose interruptions or discontinuations, while maintaining quality of life and dosing. There is precedent for this concept, as the tumor necrosis  $\alpha$  (TNF) inhibitor infliximab is recommended for the treatment of ICI-related colitis and the IL-6 inhibitor tocilizumab has been approved for the treatment of cytokine release syndrome related to chimeric antigen receptor T (CAR-T) therapies in cancer (Buder-Bakhaya et al, Front Immunol 2018). At MSKCC we have reported the efficacy of agents targeting IL12/23, IL4/13, CD20, and IgE in patients treated with cutaneous AEs related to immunotherapies, which has allowed continued administration of the culprit medication (Phillips et al, J Clin Oncol 2019).

Our current single-arm trial investigating the treatment of grade 2/3 eosinophil related AEs includes 17 patients with grade 2/3 alpelisib rashes

who were treated with benralizumab in a reactive fashion (#20-344 IIT, PI [name]). Patients continued on alpelisib while on the trial. All 17 patients showed therapeutic response, defined as a reduction in eosinophil related AE grade  $\leq 1$  at week 4 post treatment initiation. Clinical response correlated with reduction in blood eosinophils to 0K/mcl at week 4 in all patients. Rash did not recur after corticosteroids were discontinued and alpelisib was rechallenged to the initial dose. No adverse events were attributed to benralizumab in this study.

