## 14.0 BIOSTATISTICS

### Sample Size

This will be a single arm trial. The target sample size is intended to test the hypothesis that benralizumab reduces the frequency of grade  $\geq$  grade 2 rash at 4 weeks relative to the historical controls in patients receiving alpelisib. The primary endpoint in the current study will be the proportion of patients to achieve a rash grade of 1 or less. It has been reported that approximately 34% of patients receiving alpelisib will develop  $\geq$  grade 2 rash within the first 30 days. An increase in rash control to approximately 88% is deemed to be clinically meaningful with the investigational agent. Sample sizes of 57 patients achieves an 80% power to detect a difference based on a two sample proportions test. Due to potential attrition during the course of the study, the sample size will be increased by 10%. The resultant sample size will be 63 patients.

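### Sections 6.1 and 6.2 do not require patients to be new to alpelisib or other PI3K inhibitors, although the 66% null rests on rash in the first 30 days on alpelisib

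*Combined protocol and SAP*

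**What the plan says.** **Eligibility.** Inclusion 2 (section 6.1) reads "Must be scheduled to receive SOC endocrine therapy (alpelisib plus fulvestrant or AIs"). It concerns planned treatment, not earlier treatment. In section 6.2, exclusion 13 removes patients with "More than 2 lines of endocrine-based therapy in the metastatic setting". Exclusion 1 removes known hypersensitivity to alpelisib, exclusion 5 deals with recent anti-IL-5 agents, and exclusion 11 leaves room for investigator judgement. None of the 12 inclusion and 13 exclusion criteria mentions earlier alpelisib or another PI3K inhibitor.

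**Benchmark.** Section 14.0, Sample Size: "It has been reported that approximately 34% of patients receiving alpelisib will develop" grade 2 or worse rash in the first 30 days. Section 1.0 turns this round: "The corollary is that 66% of historical controls will have grade" 1 or lower over that period. The target is in section 14.0: "An increase in rash control to approximately 88% is deemed to be clinically meaningful with the investigational agent". The trial has a single arm.

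**Timing of rash.** Section 3.4 reports from the lead centre's experience that "90% of rash develops within the first 4 weeks".

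**The concern.** With no concurrent control, the efficacy conclusion depends on the enrolled patients having, without benralizumab, the same 66% chance of success as the historical patients. That figure describes the opening weeks of alpelisib, which is when the protocol says most rash appears. The natural reading is a first course.

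A patient who took alpelisib in an earlier line and now restarts it carries information that a new patient does not: rash either appeared the first time or it did not. Such a patient's background risk may be lower or higher than 34%. The criteria let the patient in, and the analysis has no means of correcting for the difference. The historical comparisons of time to rash and of four-week relative dose intensity would carry the same mismatch.

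**Working it through.** **1. The plan's own figure.** Section 14.0 states: "Sample sizes of 57 patients achieves an 80% power to detect a difference based on a two sample proportions test". Inputs are p0 = 0.66, p1 = 0.88 and power 80%. Alpha is not stated; two-sided 0.05 is assumed because it reproduces the plan's number. With mean proportion 0.77:

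n = [1.960·√(2·0.77·0.23) + 0.842·√(0.66·0.34 + 0.88·0.12)]² / (0.88 − 0.66)²
= [1.960·0.595 + 0.842·0.574]² / 0.0484 ≈ 2.72 / 0.0484 ≈ 56.2, rounded up to **57** (power 0.805).

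Then 57 × 1.10 = 62.7, giving **63** enrolled. Both figures reproduce. Neither depends on prior exposure.

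**2. Search for a rule on prior exposure.**

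| Place | What it controls | Bars prior PI3K inhibitor? |
|---|---|---|
| Inclusion 2 | treatment about to be given | no |
| Exclusion 1 | known hypersensitivity | only if an earlier reaction carries that label |
| Exclusion 11 | investigator's view of suitability | not as a rule |
| Exclusion 13 | number of endocrine-based lines | no |
| Sections 10.0 and 11.0 | alpelisib starts on day 1 | no; this is a schedule |

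Section 4.1 states a limit of one prior line where exclusion 13 allows two. Either limit leaves the content of a line open.

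**3. Illustration of size.** The documents give no decision rule, no count of re-exposed patients and no rash rate for them, so all three are assumed.

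- Rule: exact one-sample binomial test against 0.66, one-sided 0.025, n = 57. The smallest qualifying count is 45, because P(X ≥ 45 | 57, 0.66) = 0.024 and P(X ≥ 44 | 57, 0.66) = 0.047.
- m re-exposed patients, each with probability q of grade 1 or lower rash; the other 57 − m have 0.66. Benralizumab has no effect in anyone.
- Average null = [(57 − m)·0.66 + m·q] / 57.
- False-positive rate = P(X₁ + X₂ ≥ 45), with X₁ ~ Bin(57 − m, 0.66) and X₂ ~ Bin(m, q), by exact convolution.

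| m | q | Average null | False-positive rate |
|---|---|---|---|
| 0 | – | 0.660 | 0.024 |
| 3 | 0.90 | (54·0.66 + 2.7)/57 = 0.673 | 0.037 |
| 6 | 0.90 | (51·0.66 + 5.4)/57 = 0.685 | 0.055 |
| 3 | 0.50 | (54·0.66 + 1.5)/57 = 0.652 | 0.017 |
| 6 | 0.50 | (51·0.66 + 3.0)/57 = 0.643 | 0.012 |

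The error rises if re-exposed patients tend to be past tolerators and falls if they tend to be prone to rash. With all 63 evaluable (rule 50 or more, nominal 0.015), the pattern is the same: 0.023 and 0.035 at q = 0.90, and 0.011 and 0.008 at q = 0.50.

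**The case against.** **The pool is probably small.** Section 10.0 continues alpelisib until the cancer progresses or toxicity becomes unacceptable. Patients who progressed on it would not obviously be planned for it again as standard care, and those who stopped for toxicity fall partly under exclusions 1 and 11. The text throughout describes giving benralizumab before alpelisib is started. All of this stands and limits the likely size. It does not close the gap, since discretion at three institutions is not a uniform rule.

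**A reader might infer that the bias must favour benralizumab**, because exclusion 1 removes some patients who reacted badly and leaves tolerators. The documents do not establish this. Someone with an earlier grade 2 rash need not have been labelled hypersensitive, so rash-prone patients can enter too, and the table above then reverses.

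**A reader might also take section 3.5 as proof that re-exposed patients succeed regardless of treatment**: "Rash did not recur after corticosteroids were discontinued and alpelisib was rechallenged to the initial dose". All 17 patients described there had received benralizumab, so the passage says nothing about tolerance without it. The timing statement in section 3.4 likewise does not show that risk stays low when alpelisib is restarted after a gap.

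**Larger error rates can be produced.** If 20% of patients are re-exposed and 95% of them are rash-free, the rate is about 0.146. Neither input has a source in the documents, and a share that high is hard to credit.

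**Exclusion 5.** It might be read as covering only anti-IL-5 agents given for asthma, which would admit patients treated with benralizumab for rash. The sentence can equally be read so that the asthma qualifier attaches only to the other biologics. It is ambiguous, not clearly limited.

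**Conclusion.** The point holds as a gap in eligibility and comparability. The written criteria admit patients previously treated with alpelisib or another PI3K inhibitor, and such patients do not match a benchmark taken from the first 30 days on alpelisib. The direction and size of the bias cannot be fixed from the documents. Under the assumed rule, up to six such patients move the false-positive rate from 0.024 to somewhere between about 0.012 and 0.055, for background success rates from 50% to 90%.

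This rests on three assumptions: the 34% rate describes a first course (the natural reading, though its source is not at hand), the decision rule is the exact one above, and a few such patients do enrol. The sample size is not affected. Exclusion 13 is not wrong in itself; it is where the missing rule would sit.

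**What to change.** 1. Add to section 6.2 and to the eligibility checklist: *Any prior treatment with alpelisib or another PI3K inhibitor.*
2. Reword exclusion 5 so that anti-IL-5 and anti-IL-5 receptor agents count for any indication, within the 12-week window it already states.
3. If a re-exposed patient has already been enrolled, keep that patient in the primary modified ITT analysis. Section 14.0 defines that population as everyone with a 4-week efficacy assessment, and removing eligible patients afterwards in an open-label trial would create a new problem. Add a labelled sensitivity analysis of the primary endpoint without them.

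Cost: one new exclusion line, one reworded criterion and, if needed, one additional analysis. Medical history is already taken at screening (Table 9). The targets stay at 57 evaluable and 63 enrolled. The downside is the loss of a few otherwise eligible patients to accrual.
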